#### **5.2.4 Trial Blinding/Masking**

This is an open-label trial; therefore, the Sponsor, investigator and subject will know the treatment administered.

#### **5.3 Randomization or Treatment Allocation**

Randomization will be discussed with participants during the process of informed consent and will occur after registration and within 7 days prior to the start of treatment. The randomization codes are generated by the study statisticians and stored in the Cancer Center Clinical Trials Database.

#### **5.4 Stratification**

No stratification planned.

#### **5.5 Concomitant Medications/Vaccinations (allowed & prohibited)**

Medications or vaccinations specifically prohibited in the exclusion criteria are not allowed during the ongoing trial. If there is a clinical indication for one of these or other medications or vaccinations specifically prohibited during the trial, discontinuation from trial therapy or vaccination may be required. The investigator should discuss any questions regarding this with the Merck Clinical team. The final decision on any supportive therapy or vaccination rests with the investigator and/or the subject's primary physician.

##### **5.5.1 Acceptable Concomitant Medications**

All treatments that the investigator considers necessary for a subject's welfare may be administered at the discretion of the investigator in keeping with the community standards of medical care. All concomitant medication will be recorded on the case report form (CRF) including all prescription, over-the-counter (OTC), herbal supplements, and IV medications and fluids. If changes occur during the trial period, documentation of drug dosage, frequency, route, and date may also be included on the CRF.

All concomitant medications received within 28 days before the first dose of trial treatment and 30 days after the last dose of trial treatment should be recorded. Concomitant medications administered after 30 days after the last dose of trial treatment should be recorded for SAEs and ECIs as defined in [Section 7.2](#).

##### **5.5.2 Prohibited Concomitant Medications**

Subjects are prohibited from receiving the following therapies during the Screening and Treatment Phase (including retreatment for post-complete response relapse) of this trial:

**Product:** Pembrolizumab

**Protocol/Amendment No.:** UVA Breast 48

V04-13-21

- Antineoplastic systemic chemotherapy or biological therapy
- Immunotherapy not specified in this protocol
- Chemotherapy not specified in this protocol
- Investigational agents other than pembrolizumab
- Radiation therapy
  - Note: Radiation therapy to a symptomatic solitary lesion or to the brain may be allowed at the investigator's discretion.
- Live vaccines within 30 days prior to the first dose of trial treatment and while participating in the trial. Examples of live vaccines include, but are not limited to, the following: measles, mumps, rubella, varicella/zoster, yellow fever, rabies, BCG, and typhoid vaccine.
- Systemic glucocorticoids for any purpose other than to modulate symptoms from an event of clinical interest of suspected immunologic etiology. The use of physiologic doses of corticosteroids may be approved after consultation with the Sponsor.

Subjects who, in the assessment by the investigator, require the use of any of the aforementioned treatments for clinical management (except glucocorticoids for irAE's) should be removed from the trial. Subjects may receive other medications that the investigator deems to be medically necessary.

The Exclusion Criteria describes other medications which are prohibited in this trial.

There are no prohibited therapies during the Post-Treatment Follow-up Phase.

## 5.6 Rescue Medications & Supportive Care

### 5.6.1 Supportive Care Guidelines

Subjects should receive appropriate supportive care measures as deemed necessary by the treating investigator. Suggested supportive care measures for the management of adverse events with potential immunologic etiology are outlined below. Where appropriate, these guidelines include the use of oral or intravenous treatment with corticosteroids as well as additional anti-inflammatory agents if symptoms do not improve with administration of corticosteroids. Note that several courses of steroid tapering may be necessary as symptoms may worsen when the steroid dose is decreased. For each disorder, attempts should be made to rule out other causes such as metastatic disease or bacterial or viral infection, which might require additional supportive care. The treatment guidelines are intended to be applied when the investigator determines the events to be related to pembrolizumab.

Note: if after the evaluation the event is determined not to be related, the investigator does not need to follow the treatment guidance (as outlined below). Refer to [Section 5.2.1](#) for dose modification.

It may be necessary to perform conditional procedures such as bronchoscopy, endoscopy, or skin photography as part of evaluation of the event.

- **Pneumonitis:**

- For **Grade 2 events**, treat with systemic corticosteroids. When symptoms improve to Grade 1 or less, steroid taper should be started and continued over no less than 4 weeks.

**Product:** Pembrolizumab

**Protocol/Amendment No.:** UVA Breast 48

V04-13-21

- For **Grade 3-4 events**, immediately treat with intravenous steroids. Administer additional anti-inflammatory measures, as needed.
- Add prophylactic antibiotics for opportunistic infections in the case of prolonged steroid administration.
- **Diarrhea/Colitis:**

Subjects should be carefully monitored for signs and symptoms of enterocolitis (such as diarrhea, abdominal pain, blood or mucus in stool, with or without fever) and of bowel perforation (such as peritoneal signs and ileus).

  - All subjects who experience diarrhea/colitis should be advised to drink liberal quantities of clear fluids. If sufficient oral fluid intake is not feasible, fluid and electrolytes should be substituted via IV infusion. For Grade 2 or higher diarrhea, consider GI consultation and endoscopy to confirm or rule out colitis.
  - For **Grade 2 diarrhea/colitis**, administer oral corticosteroids.
  - For **Grade 3 or 4 diarrhea/colitis**, treat with intravenous steroids followed by high dose oral steroids.
  - When symptoms improve to Grade 1 or less, steroid taper should be started and continued over no less than 4 weeks.
- **Hypophysitis:**
  - For **Grade 2** events, treat with corticosteroids. When symptoms improve to Grade 1 or less, steroid taper should be started and continued over no less than 4 weeks. Replacement of appropriate hormones may be required as the steroid dose is tapered.
  - For **Grade 3-4** events, treat with an initial dose of IV corticosteroids followed by oral corticosteroids. When symptoms improve to Grade 1 or less, steroid taper should be started and continued over no less than 4 weeks. Replacement of appropriate hormones may be required as the steroid dose is tapered.
- **Hyperthyroidism or Hypothyroidism:**

Thyroid disorders can occur at any time during treatment. Monitor patients for changes in thyroid function (at the start of treatment, periodically during treatment, and as indicated based on clinical evaluation) and for clinical signs and symptoms of thyroid disorders.

  - **Grade 2** hyperthyroidism events (and **Grade 2-4** hypothyroidism):
    - In hyperthyroidism, non-selective beta-blockers (e.g. propranolol) are suggested as initial therapy.
    - In hypothyroidism, thyroid hormone replacement therapy, with levothyroxine or liothyroinine, is indicated per standard of care.
  - **Grade 3-4** hyperthyroidism
    - Treat with an initial dose of IV corticosteroid followed by oral corticosteroids. When symptoms improve to Grade 1 or less, steroid taper should be started and continued over no less than 4 weeks. Replacement of appropriate hormones may be required as the steroid dose is tapered.
- **Hepatic:**

**Product:** Pembrolizumab

**Protocol/Amendment No.:** UVA Breast 48

V04-13-21

- For **Grade 2** events, monitor liver function tests more frequently until returned to baseline values (consider weekly).
  - Treat with IV or oral corticosteroids
- For **Grade 3-4** events, treat with intravenous corticosteroids for 24 to 48 hours.
- When symptoms improve to Grade 1 or less, a steroid taper should be started and continued over no less than 4 weeks.
- **Nephritis:**
  - For **Grade 2** events, treat with corticosteroids.
  - For **Grade 3-4** events, treat with systemic corticosteroids.
  - When symptoms improve to Grade 1 or less, steroid taper should be started and continued over no less than 4 weeks.
- **Management of Infusion Reactions:** Signs and symptoms usually develop during or shortly after drug infusion and generally resolve completely within 24 hours of completion of infusion.

Table 5 below shows treatment guidelines for subjects who experience an infusion reaction associated with administration of pembrolizumab (MK-3475).

Table 5: Infusion Reaction Treatment Guidelines

NCI CTCAE Grade	Treatment	Premedication at subsequent dosing
Grade 1 Mild reaction; infusion interruption not indicated; intervention not indicated	Increase monitoring of vital signs as medically indicated until the subject is deemed medically stable in the opinion of the investigator.	None
Grade 2 Requires infusion interruption but responds promptly to symptomatic treatment (e.g., antihistamines, NSAIDS, narcotics, IV fluids); prophylactic medications indicated for <=24 hrs	Stop Infusion and monitor symptoms. Additional appropriate medical therapy may include but is not limited to: IV fluids Antihistamines NSAIDS Acetaminophen Narcotics  Increase monitoring of vital signs as medically indicated until the subject is deemed medically stable in the opinion of the investigator. If symptoms resolve within one hour of stopping drug infusion, the infusion may be restarted at 50% of the original infusion rate (e.g., from 100 mL/hr to 50 mL/hr). Otherwise dosing will be held until symptoms resolve and the subject should be premedicated for the next scheduled dose. Subjects who develop Grade 2 toxicity despite adequate premedication should be permanently discontinued from further trial treatment administration.	Subject may be premedicated 1.5h ( $\pm$ 30 minutes) prior to infusion of pembrolizumab (MK-3475) with:  Diphenhydramine 50 mg po (or equivalent dose of antihistamine).  Acetaminophen 500-1000 mg po (or equivalent dose of antipyretic).
Grades 3 or 4  Grade 3: Prolonged (i.e., not rapidly responsive to symptomatic medication and/or brief interruption of infusion); recurrence of symptoms following initial improvement; hospitalization indicated for other clinical sequelae	Stop Infusion. Additional appropriate medical therapy may include but is not limited to: IV fluids Antihistamines NSAIDS Acetaminophen Narcotics Oxygen	No subsequent dosing

**Product:** Pembrolizumab

**Protocol/Amendment No.:** UVA Breast 48

V04-13-21

NCI CTCAE Grade	Treatment	Premedication at subsequent dosing
(e.g., renal impairment, pulmonary infiltrates)  Grade 4: Life-threatening; pressor or ventilatory support indicated	Pressors Corticosteroids Epinephrine  Increase monitoring of vital signs as medically indicated until the subject is deemed medically stable in the opinion of the investigator. Hospitalization may be indicated. Subject is permanently discontinued from further trial treatment administration.	
Appropriate resuscitation equipment should be available in the room and a physician readily available during the period of drug administration.		

## 5.7 Diet/Activity/Other Considerations

### 5.7.1 Diet

Subjects should maintain a normal diet unless modifications are required to manage an AE such as diarrhea, nausea or vomiting.

### 5.7.2 Contraception

Pembrolizumab may have adverse effects on a fetus in utero. Furthermore, it is not known if pembrolizumab has transient adverse effects on the composition of sperm.

For this trial, male subjects will be considered to be of non-reproductive potential if they have azoospermia (whether due to having had a vasectomy or due to an underlying medical condition).

Female subjects will be considered of non-reproductive potential if they are either:

(1) postmenopausal (defined as at least 12 months with no menses without an alternative medical cause; in women < 45 years of age a high follicle stimulating hormone (FSH) level in the postmenopausal range may be used to confirm a post-menopausal state in women not using hormonal contraception or hormonal replacement therapy. In the absence of 12 months of amenorrhea, a single FSH measurement is insufficient.);

OR

(2) have had a hysterectomy and/or bilateral oophorectomy, bilateral salpingectomy or bilateral tubal ligation/occlusion, at least 6 weeks prior to screening;

OR

(3) has a congenital or acquired condition that prevents childbearing.

Female and male subjects of reproductive potential must agree to avoid becoming pregnant or impregnating a partner, respectively, while receiving study drug and for 120 days after the last dose of study drug by complying with one of the following:

(1) practice abstinence† from heterosexual activity;

**Product:** Pembrolizumab

**Protocol/Amendment No.:** UVA Breast 48

V04-13-21

OR

(2) use (or have their partner use) acceptable contraception during heterosexual activity.

Acceptable methods of contraception are‡:

Single method (one of the following is acceptable):

- intrauterine device (IUD)
- vasectomy of a female subject's male partner
- contraceptive rod implanted into the skin

Combination method (requires use of two of the following):

- diaphragm with spermicide (cannot be used in conjunction with cervical cap/spermicide)
- cervical cap with spermicide (nulliparous women only)
- contraceptive sponge (nulliparous women only)
- male condom or female condom (cannot be used together)
- hormonal contraceptive: oral contraceptive pill (estrogen/progestin pill or progestin-only pill), contraceptive skin patch, vaginal contraceptive ring, or subcutaneous contraceptive injection

†Abstinence (relative to heterosexual activity) can be used as the sole method of contraception if it is consistently employed as the subject's preferred and usual lifestyle and if considered acceptable by local regulatory agencies and ERCs/IRBs. Periodic abstinence (e.g., calendar, ovulation, symptothermal, post-ovulation methods, etc.) and withdrawal are not acceptable methods of contraception.

‡If a contraceptive method listed above is restricted by local regulations/guidelines, then it does not qualify as an acceptable method of contraception for subjects participating at sites in this country/region.

Subjects should be informed that taking the study medication may involve unknown risks to the fetus (unborn baby) if pregnancy were to occur during the study. In order to participate in the study subjects of childbearing potential must adhere to the contraception requirement (described above) from the day of study medication initiation (or 14 days prior to the initiation of study medication for oral contraception) throughout the study period up to 120 days after the last dose of trial therapy. If there is any question that a subject of childbearing potential will not reliably comply with the requirements for contraception, that subject should not be entered into the study.

### **5.7.3 Use in Pregnancy**

If a subject inadvertently becomes pregnant while on treatment with pembrolizumab, the subject will immediately be removed from the study. The site will contact the subject at least monthly and document the subject's status until the pregnancy has been completed or terminated. The outcome of the pregnancy will be reported to the Sponsor and to Merck without delay and within 24 hours to the Sponsor and within 2 working days to Merck if the outcome is a serious adverse experience (e.g., death, abortion, congenital anomaly, or other disabling or life-threatening complication to the mother or newborn).

The study investigator will make every effort to obtain permission to follow the outcome of the pregnancy and report the condition of the fetus or newborn to the Sponsor. If a male subject impregnates his female partner the study personnel at the site must be informed immediately and the pregnancy reported to the Sponsor and to Merck and followed as described above and in [Section 7.2.5](#).

**Product:** Pembrolizumab

**Protocol/Amendment No.:** UVA Breast 48

V04-13-21

#### **5.7.4 Use in Nursing Women**

It is unknown whether pembrolizumab is excreted in human milk. Since many drugs are excreted in human milk, and because of the potential for serious adverse reactions in the nursing infant, subjects who are breast-feeding are not eligible for enrollment.

#### **5.8 Subject Withdrawal/Discontinuation Criteria**

Subjects may withdraw consent at any time for any reason or be dropped from the trial at the discretion of the investigator should any untoward effect occur. In addition, a subject may be withdrawn by the investigator or the Sponsor if enrollment into the trial is inappropriate, the trial plan is violated, or for administrative and/or other safety reasons. Specific details regarding discontinuation or withdrawal are provided in [Section 7.1.5 – Other Procedures](#).

A subject must be discontinued from the trial for any of the following reasons:

- The subject or legal representative (such as a parent or legal guardian) withdraws consent.
- Confirmed radiographic disease progression

*Note:* A subject may be granted an exception to continue on treatment with confirmed radiographic progression if clinically stable or clinically improved, please see [Section 5.8.1](#)

- Unacceptable adverse experiences as described in [Section 5.2.2](#).
- Intercurrent illness that prevents further administration of treatment
- Investigator's decision to withdraw the subject
- The subject has a confirmed positive serum pregnancy test
- Noncompliance with trial treatment or procedure requirements
- The subject is lost to follow-up
- Completed 24 months of uninterrupted treatment with pembrolizumab or 35 administrations of study medication, whichever is later.

*Note: 24 months of study medication is calculated from the date of first dose. Subjects who stop pembrolizumab after 24 months may be eligible for up to one year of additional study treatment if they progress after stopping study treatment provided they meet the requirements detailed in [Section 7.1.6.5](#).*

- Administrative reasons

The End of Treatment and Follow-up visit procedures are listed in [Section 6](#) (Protocol Flow Chart) and [Section 7.1.6](#) (Visit Requirements). After the end of treatment, each subject will be followed for 30 days for adverse event monitoring (serious adverse events will be collected for 90 days after the end of treatment as described in [Section 7.2](#)). Subjects who discontinue for reasons other than progressive disease will have post-treatment follow-up for disease status until disease progression, initiating a non-

**Product:** Pembrolizumab

**Protocol/Amendment No.:** UVA Breast 48

V04-13-21

study cancer treatment, withdrawing consent or becoming lost to follow-up. After documented disease progression each subject will be followed by telephone for overall survival until death, withdrawal of consent, or the end of the study, whichever occurs first.

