## 5.2 Trial Treatments

The treatment to be used in this trial is outlined below in Table 3: Trial Treatment

Table 3: Trial Treatment

Arm	Drug	Dose	Dose Frequency	Route of Administration	Regimen/Treatment Period	Use
A	Pembrolizumab	200 mg	Q3W	IV infusion	Days 22, 43, 64 and Day 1 of each ensuing 3 week cycle	Experimental
B	Pembrolizumab	200 mg	Q3W	IV infusion	Days 1, 22, 43, 64 and Day 1 of each ensuing 3 week cycle	Experimental
A/B	Focused Ultrasound Tumor ablation 				Day 15	Experimental

Focused Ultrasound ablation should target 50% of the tumor, up to 3 cubic centimeters, not the entire tumor volume. See eligibility criteria for minimum tumor size parameters. There is no maximum tumor size parameter. See also section 5.2.1.2.

Trial treatment should begin on the day of randomization or as close as possible to the date on which treatment is allocated/assigned.

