**Note: Non-irAE will be managed as appropriate, following clinical practice recommendations.**

a AST/ALT: >3.0 to 5.0 x ULN if baseline normal; >3.0 to 5.0 x baseline, if baseline abnormal; bilirubin:>1.5 to 3.0 x ULN if baseline normal; >1.5 to 3.0 x baseline if baseline abnormal

b AST/ALT: >5.0 to 20.0 x ULN, if baseline normal; >5.0 to 20.0 x baseline, if baseline abnormal; bilirubin:>3.0 to 10.0 x ULN if baseline normal; >3.0 to 10.0 x baseline if baseline abnormal

c AST/ALT: >20.0 x ULN, if baseline normal; >20.0 x baseline, if baseline abnormal; bilirubin: >10.0 x ULN if baseline normal; >10.0 x baseline if baseline abnormal

d The decision to withhold or permanently discontinue pembrolizumab is at the discretion of the investigator or treating physician. If control achieved or  $\leq$  Grade 2, pembrolizumab may be resumed.

e Events that require discontinuation include, but are not limited to: encephalitis and other clinically important irAEs (eg, vasculitis and sclerosing cholangitis).

Dosing interruptions are permitted in the case of medical / surgical events or logistical reasons not related to study therapy (e.g., elective surgery, unrelated medical events, patient vacation, and/or holidays). Subjects should be placed back on study therapy within 3 weeks of the scheduled interruption, unless otherwise discussed with the Sponsor. The reason for interruption should be documented in the patient's study record

Note: There is no dose modification for HIFU as it is only administered once in this protocol.

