### **7.1.5 Other Procedures**

#### **7.1.5.1 Withdrawal/Discontinuation**

When a subject discontinues/withdraws prior to trial completion, all applicable activities scheduled for the final trial visit should be performed at the time of discontinuation. Any adverse events which are present at the time of discontinuation/withdrawal should be followed in accordance with the safety requirements outlined in [Section 7.2](#) - Assessing and Recording Adverse Events. Subjects who a) attain a CR or b) complete 24 months of treatment with pembrolizumab may discontinue treatment with the option of restarting treatment if they meet the criteria specified in [Section 7.1.6.5](#). After discontinuing treatment following assessment of CR, these subjects should return to the site for a Safety Follow-up Visit (described in [Section 7.1.6.3.1](#)) and then proceed to the Follow-Up Period of the study (described in [Section 7.1.6.4](#)).

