### **7.2.10 Dose Limiting Toxicities**

A DLT of pembrolizumab is defined as an unacceptable, drug-related toxicity requiring permanent discontinuation, per [Table 4](#) (Dose Modification Guidelines for Drug-Related Adverse Events).

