## 8.2 Statistical Analysis Plan

Target sample size is 12 participants, which was chosen as a feasible number that could be accrued within a 2 year accrual period. Participants will be randomized 1:1 to treatment arms A and B with block randomization using blocks of size 2 or 4. Participants are considered evaluable if they satisfy all inclusion and exclusion criteria and have adequate endpoint measurements during respective cohort timelines. Adjusting for a 10% unevaluable/drop-out rate, maximum target accrual is estimated at 15 participants.

The purpose is to assess the adverse events profile of pembrolizumab and focused ultrasound therapy and estimate the difference in the TILs at baseline and 3 weeks within each arm, not to make definitive comparisons between arms. With 6 participants per arm, there is limited power to make comparisons between arms. Lu et. al. (2009) data estimates the difference in means of the ratio of CD4+ and CD8+ cells for patients treated with HIFU versus no HIFU to be 0.57, with standard deviations ranging from 0.27 to 0.40. These data provide an indication of the magnitude that could be detected in this study at baseline and 3 weeks, where it is assumed that the no HIFU participants in Lu et. al. are comparable to baseline measurements in our study. Using these data as a guideline, with n=6, we have 80% power to detect an effect size of 1.44 for the within-arm change in ratio of CD4+ and CD8+ cells at baseline and 3 weeks. Depending on the variability of the data, this is equivalent to detecting differences of 0.39 and 0.58, for assumed standard deviations of 0.27 and 0.40, respectively. The populations will include all intention to treat participants.

Safety stopping rules will be employed within each arm and will be judged by dose limiting toxicities (DLT). If the first two participants within an arm or 3 out of the 6 participants within an arm experience a DLT, that arm will be deemed too toxic and further accrual to that arm will be closed. This decision rule is based on Wald's sequential probability ratio test assuming lower and upper DLT proportions of 0.1 and 0.3, respectively, and type I and II error rates of 10%.

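### A permanent stop for pembrolizumab toxicity in cycle 1 can leave the Day 22 primary-endpoint biopsy missing in Arm B only, because the protocol does not separate stopping the drug from ending data collection

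*Combined protocol and SAP*

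**What the plan says.** **What ends participation.** Section 5.8 introduces its reasons with "A subject must be discontinued from the trial for any of the following reasons". One of them is "Unacceptable adverse experiences as described in" Section 5.2.2. That section does not define the term. The nearest definition is in Section 7.2.10: "A DLT of pembrolizumab is defined as an unacceptable, drug-related toxicity requiring permanent discontinuation, per" Table 4.

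**What happens then.** Section 7.1.5.1 says that "all applicable activities scheduled for the final trial visit should be performed at the time of discontinuation". In the Section 6.1 flow charts for both arms, the discontinuation and follow-up columns contain no tumor biopsy and no correlative blood. Section 5.8 continues follow-up for adverse events, disease status and survival.

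**Timing.** Under Section 2.1, Arm B is first dosed on Day 1 and Arm A on Day 22. Both arms have HIFU on Day 15 and biopsies on Days 1 and 22, the biopsies being planned for every patient. Section 5.2.3 puts each dose after that day's procedures.

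**Analysis.** Section 8.2 states: "The populations will include all intention to treat participants". It also defines an evaluable participant as one with adequate endpoint measurements, and it gives no rule for missing values.

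**Drug stop and HIFU.** For a Grade 3 or 4 infusion reaction, Table 5 (Section 5.6.1) says: "Subject is permanently discontinued from further trial treatment administration". Section 5.2 says: "The treatment to be used in this trial is outlined below in Table 3: Trial Treatment", and that table lists HIFU alongside pembrolizumab. Table 4 acts on pembrolizumab alone.

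**The concern.** Before the Day 22 biopsy, only Arm B can have pembrolizumab toxicity. If a permanent stop also ends scheduled data collection, the primary measurement goes missing in one randomised arm because of a post-randomisation reaction to the drug. That reaction is plausibly related to the immune activation being measured, so the missing values may not resemble the observed ones.

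The two within-arm changes, HIFU alone in Arm A and the combination in Arm B, are the main product of this pilot. One of them can be selected on drug toxicity and the other cannot. Randomisation does not protect against that.

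**Working it through.** **1. Do the sections agree on what is discontinued?**
- Section 5.8 says the trial.
- Section 5.8.1 describes confirmed progression, also on the Section 5.8 list, as discontinuation from study therapy.
- Section 7.1.6.2 cites Section 5.8 for stopping treatment, but Section 7.1.6.2.1 places the End of Treatment visit at discontinuation from the study.
- Section 5.8 itself keeps these subjects in follow-up.

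The terms are used interchangeably. No section says whether the Day 15 HIFU, the Day 22 biopsy or the Day 22 research blood still takes place after a drug stop.

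**2. Which arm is exposed?** Arm B has 21 days (Day 1 to Day 22) in which drug toxicity can precede the biopsy. Arm A has none, because its first dose follows the Day 22 procedures. HIFU events and the other Section 5.8 reasons can affect either arm.

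**3. Reproduce the plan's power.** Inputs from Section 8.2: n = 6 per arm, effect size 1.44, power 80%. The significance level is not stated. Two-sided 5% is assumed because it reproduces the figure. For a paired t-test with n − 1 = 5 degrees of freedom and noncentrality 1.44 × √6, power is 80.3%, and the effect detectable with 80% power is 1.435. In ratio units, 1.44 × 0.27 = 0.39 and 1.44 × 0.40 = 0.58, as stated.

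**4. The same test with fewer Day 22 biopsies**

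| Evaluable in Arm B | Power at 1.44 | Effect detectable with 80% power |
|---|---|---|
| 6 | 80.3% | 1.44 |
| 5 | 67.7% | 1.68 |
| 4 | 50.3% | 2.13 |

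**5. Chance of a loss.** Let q be the probability that an Arm B participant has a permanent-stop toxicity before the Day 22 biopsy. The documents give no value. The proportions 0.1 and 0.3 in Section 8.2 are overall DLT bounds for the stopping rule, not cycle-1 rates. The chance of losing at least one of 6 is 1 − (1 − q)^6. Expected power weights the power at each number remaining by its binomial probability.

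| Assumed q | At least 1 of 6 lost | Expected power at 1.44 |
|---|---|---|
| 2% | 11.4% | 78.8% |
| 5% | 26.5% | 76.3% |
| 10% | 46.9% | 72.1% |

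**6. Effect of accrual to 15.** With 1:1 allocation, each arm would have 7 or 8. With 7 in Arm B, fewer than 6 remain if at least 2 are lost: 1 − (1 − q)^7 − 7q(1 − q)^6 = 0.8%, 4.4% and 15% at q = 2%, 5% and 10%.

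**7. Selection.** The shift in Arm B's mean change is the fraction lost times the difference between those who remain and those lost. For 1 of 6 lost and an assumed difference of 0.5 to 1.5 SD, the shift is 0.08 to 0.25 SD. With SDs of 0.27 and 0.40, that is 0.02 to 0.10 ratio units. The direction is unknown, and enrolling more participants does not remove it.

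**The case against.** The strongest reply is that this is loose terminology. Section 2.1 plans the Day 22 biopsy for all patients without exception, Section 5.8 continues follow-up, and Section 7.1.5.1 adds final-visit activities without saying that they replace scheduled ones. This stands against a reading a reader might take from Section 5.8, that participation ends outright. It does not settle the matter: nothing schedules the biopsy after discontinuation, and a site following the flow chart would not take it.

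A reader might also infer that Arm B's result would be limited to those who tolerated the drug. The documents do not support that. Table 4 only withholds for many events, including a first Grade 3 colitis, and for some severe ones its footnote says "The decision to withhold or permanently discontinue pembrolizumab is at the discretion of the investigator or treating physician". Those participants stay in.

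A third tempting reading is that Table 5 cancels HIFU. That is weak: Table 5 concerns infusion reactions, its adjoining cell speaks only of later dosing, and Section 5.2.3 uses the same term for the dose at the start of each cycle. The wording is unresolved rather than decisive.

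Nor do missing values contradict the intention-to-treat statement. Exclusion from the analysis is an inference from the evaluable definition.

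Section 5.9.1 does not name a dosed participant as replaceable, but the over-accrual in Section 8.2 can make up the number. Section 8 also disclaims definitive between-arm comparison. Both points reduce the power consequence and leave the selection in Arm B's own estimate.

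Finally, a retained biopsy helps only participants who received HIFU. A stop on Days 1 to 15 covers 14 of the 21 days and may leave no ablation zone. Table 4 pairs many permanent-stop events with corticosteroids, which may affect the value. Both limits stand.

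**Conclusion.** The concern holds in a limited form. The plan does not distinguish stopping pembrolizumab from ending data collection, and it schedules no endpoint sampling after discontinuation. Because only Arm B is dosed before Day 22, a permanent-stop toxicity in cycle 1 can leave the primary endpoint missing in that arm alone. Arm B's estimate would then describe participants without a permanent-stop toxicity by Day 22.

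The size rests on assumed cycle-1 rates. At 2% the expected cost in power is small, from 80.3% to 78.8%. At 10% there is nearly an even chance of losing at least one of 6. The fall to 68% applies only if Arm B ends with 5 evaluable, which accrual to 15 may prevent. The selection remains in either case, with unknown direction. This is a cheap improvement to the protocol, not a flaw that invalidates the design.

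**What to change.** - Reconcile Sections 5.8, 5.8.1, 7.1.5.1 and 7.1.6.2 so that stopping study drug is distinguished from ending data collection.
- State in those sections and in the flow charts that, after a drug stop, the already scheduled Day 22 biopsy remains due from participants who received HIFU, and the Day 22 research blood from everyone randomised, where clinically safe and the participant agrees.
- In Section 8.2, specify analysis by assigned arm and reporting of missing Day 22 values by arm and reason, noting corticosteroid use before sampling.
- Reconcile Table 5 with Table 4 on whether a drug stop also cancels HIFU. That clinical decision is the sponsor's, and none is proposed here.

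The cost is amendment wording, with no procedure beyond those already scheduled. A few participants who have stopped the drug would still be asked for a biopsy they had consented to, and some of those values may be affected by steroids. The change reduces the arm-specific missingness. It cannot recover an ablation-zone value from someone who never received HIFU.
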